1.6 ESTIMATED REPORT DATE

November 2016

1.7 CHANGE HISTORY

Document Change History			
Version	Originator	Description of Change(s)	Date
1.0	[name]	New Protocol	17 MAY 2016
2.0	[name]	Corrected error in Lens Fit Assessment section at Visit 1. Changed lens material to methafilcon A and supplier to No7 Contact Lenses. Changed intermediate peripheral acuity eccentricity from 12.5° to 10° to avoid blind spot. Clarified visual acuity procedures in section 4.7.1 to be consistent with objectives section.	22 SEPT 2016

1.8 PROTOCOL SYNOPSIS

Protocol Number and Title: CR-5856 Evaluation Of The Effects Of a Black Annulus Within a Hydrogel Contact Lens on Visual Performance
Sponsor: JJVCI, [name]
Test Articles: Custom made CE marked commercially available hydrogel contact lenses with 1mm wide black annulus and 6mm inner diameter made from methafilcon A material by No7 Contact Lenses (Test). CE marked hydrogel contact lenses made from methafilcon A material by No7 Contact Lenses (Control). The design of the control contact lens is identical to the test contact lens, except that the test lens has the black annular ring.
Regimen and Dosing: At the fitting visit (Visit 1), up to two pairs of Fitting lenses will be trialed for approximately 20 to 30 minutes each for the purposes of determining the optimum study lens parameters and familiarization with the study procedures. Subjects will wear 2 of 2 study contact lenses (Test/Control or Control/Test per the randomization scheme) for a wearing time of approximately three to four hours at each of the two measurement visits (Visits 2 and 3), with the subjects remaining at the clinical site for the duration of the visits.
Phase or Type of Study: Pilot Study

Primary Objective:

The primary objective of the study will be to measure the binocular functional visual performance of the test and control contact lenses under distance day time conditions (250 cd/m²) for centrally presented high contrast (HC) time controlled visual acuity (TCVA) targets.

Secondary Objective:

The secondary objectives of the study will be to measure the binocular functional visual performance of the test and control contact lenses for the following conditions:

- i. Distance night time conditions (2.5 cd/m²) for centrally presented HC TCVA targets;
- ii. Intermediate vision indoor conditions (50cd/m²) for centrally presented HC TCVA targets.

Additional Measurements:

In addition to the primary and secondary objectives, the following will be measured:

- i. Monocular functional visual performance for centrally presented high contrast (HC) time controlled visual acuity (TCVA) targets.
 - a. Distance day time conditions (250 cd/m²)
 - b. Distance night time conditions (2.5 cd/m²)
 - c. Intermediate vision indoor conditions (50cd/m²)
- ii. Distance monocular and binocular functional visual performance of the test and control contact lenses under night time conditions (2.5 cd/m²) for HC TCVA targets presented at 5° eccentricity;
- iii. Intermediate vision monocular and binocular functional visual performance of the test and control contact lenses under indoor conditions (50cd/m²) for HC TCVA targets presented at 5° eccentricity;
- iv. Distance monocular and binocular functional visual performance of the test and control contact lenses under night time conditions (2.5 cd/m²) for decreasing contrast targets presented at 20° eccentricity;
- v. Intermediate vision monocular and binocular functional visual performance of the test and control contact lenses under indoor conditions (50cd/m²) for decreasing contrast targets presented at 10° eccentricity;
- vi. Monocular and binocular horizontal visual fields when wearing the test and control contact lenses with an Esterman perimetry test.
- vii. Subjective rating of performance following driving simulation while wearing test and control contact lenses under night time conditions;
- viii. Subjective rating of performance following PC based reaction time game while wearing test and control contact lenses.

Study Design: The study will be a bilateral, subject-masked, randomized, 2x2 cross-over, non-dispensing pilot study involving three clinic visits. Investigators who collect measurements for primary and secondary endpoints will also be masked to the identity of the study lenses. Each subject will be assigned to a unique sequence of the lens types per the randomization scheme (Test/Control or Control/Test). Lenses will be worn for approximately three to four hours each with a 2-14 day washout period in between lenses.

Sample Size: A minimum of 20 eligible subjects are targeted to complete the study as the cohort population. Subjects who are found to be ineligible, or who are discontinued or incomplete, will be classified as the non-cohort population. The total number of subjects enrolled may not exceed 25 subjects,

except by joint agreement of the Investigator and Sponsor.

Eligibility Criteria:

Subjects should meet all study Inclusion Criteria as outlined below:

- 1) Healthy adult males or females 35 to 42 years of age (inclusive) with signed informed consent.
- 2) The subject is a current spherical soft contact lens wearer (defined as a minimum of 6 hours of DW for a minimum of 1 month prior to the study).
- 3) The subject's optimal vertexed spherical equivalent distance correction must be between -6.00 and +4.00 D (inclusive).
- 4) Any cylinder power must be $\leq 0.75D$.
- 5) The subject must have visual acuity best correctable to 20/30 or better for each eye.
- 6) The subject must read and sign the Informed Consent form.
- 7) The subject must appear able and willing to adhere to the instructions set forth in this clinical protocol.

Subjects meeting any of the following Exclusion Criteria will not be eligible to participate in the study:

- 1) Currently pregnant or lactating,
- 2) Any ocular or systemic allergies or diseases that may interfere with contact lens wear.
- 3) Any infectious disease (e.g., hepatitis, tuberculosis) or a contagious immunosuppressive disease (e.g., HIV) by self-report).
- 4) Clinically significant (grade 3 or 4) corneal edema, corneal vascularization, corneal staining, or any other abnormalities of the cornea which would contraindicate contact lens wear.
- 5) Clinically significant (grade 3 or 4) tarsal abnormalities or bulbar injection which might interfere with contact lens wear.
- 6) Any ocular infection.
- 7) Any previous, or planned, ocular or intraocular surgery (e.g., radial keratotomy, PRK, LASIK, etc.).
- 8) Any corneal distortion resulting from previous hard or rigid gas permeable contact lens wear.
- 9) Habitual contact lens type is toric, bifocal, in monovision contact lens wear, or is worn as extended wear.
- 10) Participation in any contact lens or lens care product clinical trial within 30 days prior to study enrollment.
- 11) Employee of investigational clinic (e.g., Investigator, Coordinator, Technician)

Stopping Rules:

The occurrence of one or more Unanticipated Adverse Device Effect (UADE), or any SAE where relationship to study agent cannot be ruled out, will result in stopping further dispensing investigational product. In the event of a UADE or SAE, the Sponsor Medical Monitor may unmask the treatment regimen of subject(s) and may discuss this with the Investigator before any further subjects are enrolled.

2.1 NAME AND DESCRIPTION OF TEST ARTICLES

The following contact lenses will be used in this study:

Test Article Form	LENSES		
	Fitting Lenses	Test	Control
Design / Description	CE marked hydrogel contact lenses	Custom made, CE marked, commercially available hydrogel contact lenses with 1mm wide black annulus and 6mm inner diameter	CE marked hydrogel contact lenses
Lot Number or Other Identifier	N/A	N/A	N/A
Manufacturer	No7 Contact Lenses	No7 Contact Lenses	No7 Contact Lenses
Packaging Form	Vial	Vial	Vial
Nominal Distance Powers (D)	-6.00DS to +4.00DS	-6.00DS to +4.00DS	-6.00DS to +4.00DS
Nominal Base Curve @ 22° C	7.70, 8.00, 8.30, 8.60, 8.90, 9.20, 9.50 mm	7.70, 8.00, 8.30, 8.60, 8.90, 9.20, 9.50 mm	7.70, 8.00, 8.30, 8.60, 8.90, 9.20, 9.50 mm
Nominal Diameter @ 22° C	13.5, 14.0, 14.5 mm	13.5, 14.0, 14.5 mm	13.5, 14.0, 14.5 mm
Material	methafilcon A	methafilcon A	methafilcon A

Fitting lenses used at Visit 1 will be selected from a pre-ordered trial set, and will be disposed of after use. The Test and Control lenses used at Visits 2 and 3 are custom-ordered for each participant, and will be disposed of after use.

2.2 SUMMARY OF FINDINGS FROM NONCLINICAL STUDIES

See package insert (Appendix B).

2.3 SUMMARY OF KNOWN RISKS AND BENEFITS TO HUMAN SUBJECTS

See package insert (Appendix B).

2.4 DESCRIPTION OF TRIAL TREATMENTS

The study will be a bilateral, subject-masked, randomized 2x2 cross-over, non-dispensing pilot study involving three clinic visits. Investigators who collect measurements for primary and secondary endpoints will also be masked to the identity of the study lenses. The subjects will attend a first Enrolment / Fitting visit to initially obtain their informed consent and evaluate the potential participants suitability to take part in the investigation. If they fulfill the investigation's inclusion and exclusion criteria, they will be enrolled, fitted with the study contact lens type to ensure than a clinically acceptable fit is achieved and trained into the testing procedures. At the completion of the visit the test and control contact lenses will be ordered. When the study contact lenses become available the subjects will then attend two test visits during which one of the study contact lens will be tested each time. The order of testing the test or control contact lens will be randomized. The participants will attend the visits not wearing contact lenses and not having worn contact lenses that day.

2.5 STATEMENT OF COMPLIANCE TO PROTOCOL, GCP, AND APPLICABLE REGULATORY GUIDELINES

This trial will be conducted in compliance with the protocol, the International Conference on Harmonization Good Clinical Practice E6 (ICH-GCP), the Declaration of Helsinki, and all applicable regulatory requirements.

2.6 DESCRIPTION OF POPULATION TO BE STUDIED, ENROLLMENT TARGETS, AND STUDY DURATION

The prospective subjects will all be subjects registered with the sites as potential study participants. They will initially be contacted by telephone, the investigation will be explained in detail and if interested an Enrolment / Fitting / Measurement visit will be scheduled. The subjects fulfilling the criteria for inclusion and exhibiting none of the exclusion criteria will be invited in a random fashion to participate in the study until the test population is achieved. Up to 25 subjects may be enrolled in order to achieve a cohort population of 20 subjects. The study is anticipated to last for approximately 4 months with each subject being involved for a period of up to 1 to 2 months, dependent upon the length of time that is required to manufacture their study lenses.

2.7 RELEVANT LITERATURE REFERENCES AND PRIOR DATA

See package insert (Appendix B).

3.1 DESCRIPTION OF OBJECTIVES AND PURPOSE

Johnson & Johnson Vision Care (JJVCI) are interested in evaluating the effects of incorporating a black annulus within a hydrogel contact lens, on functional visual performance. The black annulus is designed to mimic the performance of a similar design. The research aims to determine whether this black annulus is likely to have any detrimental effect on vision for the wearer. This pilot study will compare the central and peripheral visual performance, including functional assessment of vision, of a test contact lens incorporating a black annulus with that of a control clear contact lens.

The primary objective of the study will be to measure the binocular functional visual performance of the test and control contact lenses under distance day time conditions (250 cd/m²) for centrally presented high contrasts (HC) time controlled visual acuity (TCVA) targets.

The secondary objectives of the study will be to measure the binocular functional visual performance of the test and control contact lenses for the following conditions:

- i. Distance night time conditions (2.5 cd/m²) for centrally presented HC TCVA targets;
- ii. Intermediate vision indoor conditions (50cd/m²) for centrally presented HC TCVA targets.

The additional study measurements will be:

- i. Monocular functional visual performance for centrally presented high contrast (HC) time controlled visual acuity (TCVA) targets.
 - a. Distance day time conditions (250 cd/m²)
 - b. Distance night time conditions (2.5 cd/m²)
 - c. Intermediate vision indoor conditions (50cd/m²)
- ii. Distance monocular and binocular functional visual performance of the test and control contact lenses under night time conditions (2.5 cd/m²) for HC TCVA targets presented at 5° eccentricity;
- iii. Intermediate vision monocular and binocular functional visual performance of the test and control contact lenses under indoor conditions (50cd/m²) for HC TCVA targets presented at 5° eccentricity;
- iv. Distance monocular and binocular functional visual performance of the test and control contact lenses under night time conditions (2.5 cd/m²) for decreasing contrast targets presented at 20° eccentricity;
- v. Intermediate vision monocular and binocular functional visual performance of the test and control contact lenses under indoor conditions (50cd/m²) for decreasing contrast targets presented at 10° eccentricity.
- vi. Monocular and binocular horizontal visual fields when wearing the test and control contact lenses with an Esterman perimetry test.
- vii. Subjective rating of performance following driving simulation while wearing test and control contact lenses under night time conditions;
- viii. Subjective rating of performance following PC based reaction time game while wearing test and control contact lenses.

4.1 PRIMARY AND SECONDARY ENDPOINTS

The primary endpoint will be measurements of binocular functional visual performance under distance day time conditions (250 cd/m²) for centrally presented high contrasts (HC) time controlled visual acuity (TCVA) targets.

The secondary endpoints will be measurements of binocular functional visual performance measured under the following conditions:

- i. Distance night time conditions (2.5 cd/m²) for centrally presented HC TCVA targets;
- ii. Intermediate vision indoor conditions (50cd/m²) for centrally presented HC TCVA targets.

The following hypotheses will be tested throughout this investigation. This is a pilot study and all the hypotheses are exploratory in nature.

Primary Study Hypothesis	
1	The binocular central distance high contrast, high illumination (250 cd/m ²) TCVA of the test lens is non-inferior to the control lens. The non-inferiority margin will be -0.5 VA units (-10 X logMAR VA).

Secondary Study Hypotheses	
1	The binocular central distance high contrast, low illumination (2.5 cd/m ²) TCVA of the test lens is non-inferior to the control lens. The non-inferiority margin will be -0.75 VA units (-10 X logMAR VA).
2	The binocular central intermediate vision high contrast, medium illumination (50 cd/m ²) TCVA of the test lens is non-inferior to the control lens. The non-inferiority margin will be -0.75 VA units (-10 X logMAR VA).

Other clinical observations:

- i. Monocular functional visual performance for centrally presented high contrast (HC) time controlled visual acuity (TCVA) targets.
 - a. Distance day time conditions (250 cd/m²)
 - b. Distance night time conditions (2.5 cd/m²)
 - c. Intermediate vision indoor conditions (50cd/m²)
- ii. Distance monocular and binocular functional visual performance of the test and control contact lenses under night time conditions (2.5 cd/m²) for HC TCVA targets presented at 5° eccentricity;
- iii. Intermediate vision monocular and binocular functional visual performance of the test and control contact lenses under indoor conditions (50cd/m²) for HC TCVA targets presented at 5° eccentricity;
- iv. Distance monocular and binocular functional visual performance of the test and control contact lenses under night time conditions (2.5 cd/m²) for decreasing contrast targets presented at 20° eccentricity;
- v. Intermediate vision monocular and binocular functional visual performance of the test and control contact lenses under conditions (50cd/m²) for decreasing contrast targets presented at 10° eccentricity.
- vi. Monocular and binocular horizontal visual fields when wearing the test and control contact lenses with an Esterman perimetry test.
- vii. Subjective rating of performance following driving simulation while wearing test and control contact lenses under night time conditions;
- viii. Subjective rating of performance following PC based reaction time game while wearing test and control contact lenses.
- ix. Biomicroscopy findings;
- x. Lens fit characteristics;
- xi. Snellen distance visual acuity;
- xii. Reasons for discontinuation;
- xiii. Reasons for unplanned lens replacement;
- xiv. Adverse events;
- xv. Lens Damage.

4.2 INCLUSION CRITERIA

Potential subjects must satisfy all of the following criteria to be enrolled in the study:

- 1) The subject must read, understand, and sign the STATEMENT OF INFORMED CONSENT and receive a fully executed copy of the form.
- 2) The subject must appear able and willing to adhere to the instructions set forth in this clinical protocol.
- 3) The subject must be between 35 and 42 years of age (inclusive).
- 4) The subject's vertex corrected spherical equivalent distance refraction must be in the range of -6.00D to +4.00D in each eye.
- 5) The subject's refractive cylinder must be $\leq 0.75D$ in each eye.
- 6) The subject must have best corrected visual acuity of 20/30 or better in each eye.
- 7) The subject must be an adapted soft contact lens wearer in both eyes (defined as a minimum of 6 hours of DW for a minimum of 1 month prior to the study).
- 8) The subject must have normal eyes (i.e., no ocular medications or infections of any type).

4.3 EXCLUSION CRITERIA

Potential subjects who meet any of the following criteria will be excluded from participating in the study:

- 1) Currently pregnant or lactating (subjects who become pregnant during the study will be discontinued).
- 2) Any ocular or systemic allergies or diseases that may interfere with contact lens wear.
- 3) Any infectious disease (e.g., hepatitis, tuberculosis) or a contagious immunosuppressive disease (e.g., HIV) by self-report.
- 4) Clinically significant (grade 3 or 4) corneal edema, corneal vascularization, corneal staining, or any other abnormalities of the cornea which would contraindicate contact lens wear.
- 5) Clinically significant (grade 3 or 4) tarsal abnormalities or bulbar injection which might interfere with contact lens wear.
- 6) Any ocular infection.
- 7) Any previous, or planned, ocular or interocular surgery (e.g., radial keratotomy, PRK, LASIK, etc.).
- 8) Any corneal distortion resulting from previous hard or rigid gas permeable contact lens wear.
- 9) Habitual contact lens type is toric, bifocal, in monovision contact lens wear, or is worn as extended wear.
- 10) Participation in any contact lens or lens care product clinical trial within 30 days prior to study enrollment.
- 11) Employee of investigational clinic (e.g., Investigator, Coordinator, Technician)

4.4 STUDY DESIGN, TIME AND EVENT SCHEDULE, FLOWCHART

The study will be a bilateral, subject-masked, randomized, 2x2 cross-over, non-dispensing pilot study involving three clinic visits. Investigators who collect measurements for primary and secondary endpoints will also be masked to the identity of the study lenses. The study will have two treatments (Test and Control) in two periods (first and second) with two randomization groups (Test/Control or Control/Test).

The participants will attend a first Enrolment / Fitting visit to initially obtain their informed consent and evaluate the potential participant's suitability to take part in the investigation. If they fulfill the investigation's inclusion and exclusion criteria, they will be enrolled, fitted with the study contact lens type to ensure that a clinically acceptable fit is achieved and trained into the testing procedures. This visit will last for approximately three hours. At the completion of the visit the test and control contact lenses will be ordered. When the study contact lenses become available the participants will then attend two test visits during which one of the study contact lens types will be tested each time. The order of testing of the test or control contact lens will be determined at random. The participants will attend the visits not wearing contact lenses and not having worn contact lenses that day. Each measurement visit will last for approximately 4.5 hours.

The participants will not take part in any concomitant investigation of any type or take concomitant medications not allowed by the exclusion criteria.

4.4.1 TIME AND EVENTS SCHEDULE

All study visits are required visits. There are no fixed time intervals between visits; however, it is anticipated that all subjects will complete both measurement visits within a period of no more than one month.

Visit 1 - Enrolment / Fitting Visit

The steps below will be followed:

- Signing of the consent form
- Participant demographics, medical and ocular history questions
- Concomitant treatments questionnaire
- Contact lens history
- Ocular symptoms
- Sphero-cylindrical refraction and BCVA
- Spherical refraction
- Ocular dominance measurement
- Keratometry
- Pupil measurement at 250, 50 & 2.5cd/m²
- HVID
- Biomicroscopy
- Eligibility
- Lens Information
- Lens Damage
- Lens Settling
- Sphero-cylindrical refraction and VA
- Lens fit assessment (including lens fit digital video recording)
- Modification
- Final contact lens prescription
- Familiarization with test measurements
- Lens Removal
- Biomicroscopy
- Sphero-cylindrical refraction and BCVA
- Continuance

Visit 2 – First Measurement Visit

The routine below will be followed:

- Concomitant treatments questionnaire
- Ocular symptoms
- Sphero-cylindrical refraction and BCVA
- Biomicroscopy
- Continuance
- Lens Randomization
- Lens Insertion
- Lens Damage
- Lens Settling
- Spherical over- refraction and VA
- Lens fit assessment (including lens fit digital video recording)
- Visual field measurement, OD, OS, OU
- Vision assessments (according to randomization scheme)
- Lens Removal
- Biomicroscopy
- Sphero-cylindrical refraction and BCVA
- Continuance

Visit 3 – Second Measurement Visit

The steps below will be followed:

- Concomitant treatments questionnaire
- Ocular symptoms
- Sphero-cylindrical refraction and BCVA
- Biomicroscopy
- Continuance
- Lens Randomization
- Lens Insertion
- Lens Damage
- Lens Settling
- Spherical over- refraction and VA
- Lens fit assessment (including lens fit digital video recording)
- Visual field measurement, OD, OS, OU
- Vision assessments (according to randomization scheme)
- Lens Removal

Final Evaluation

- Biomicroscopy
- Snellen VA measurement with spectacle refraction (Sphero-cylindrical)
- Final Evaluation Form

4.5 RANDOMIZATION AND MASKING

The lenses will not be dispensed and will be worn in a bilateral and random fashion using a 2x2 cross-over design. Permuted block randomization will be used to minimize the potential for treatment imbalance. A block size of two (2) will be utilized. A computer-generated randomization scheme will be provided by the study biostatistician to randomly assign subjects to one of two possible lens wear sequences (Test/Control or Control/Test) in a 1:1 manner. The order of applied distance as well as luminance within distance (if applicable) during vision assessments will also be randomized for each subject within lens type. The same orders applied for the first lens type will be used for the second lens type.

The random scheme will be generated using the PROC PLAN procedure from SAS Software Version 9.4 or higher (SAS Institute, Cary, NC).

The study site must follow the randomization scheme provided and complete the enrollment according to the randomization list and not pre-select or assign subjects. The randomized assignment of subjects will be performed at the beginning of Visit 2. The following must have occurred prior to randomization:

- Informed consent has been obtained
- Subject meets all the inclusion / exclusion criteria
- Subject history and baseline information has been collected

This is a subject-masked study. Study participants will be masked with respect to the sequence of study lens wear to which they have been assigned. An unmasked investigator will insert and remove the study lenses so that the subject is not aware of the study lens type. The identity of the study lenses will be unmasked to the investigator who will record the lens fitting measurements. However, the identity of the study lenses will be masked to the investigator who will collect measurements for the study primary and secondary endpoints.

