6.	Randomization	Study Lens Type will be selected based on the Randomization Scheme	
7.	Study lens insertion	The initial study contact lenses will be selected based upon the randomization schedule. Place the lenses on the subject eyes.	
8.	Lens Damage	Inspect the lenses on eye with the biomicroscope for damage and if damaged, record the damage and have the subject insert a new lens. Save worn, damaged lenses in sterile saline in the labeled vials provided with the study materials and complete the quality product complaint form.	
9.	Lens Settling	Allow the lenses to settle for at least 15 minutes.	
10.	Spherical Over-Refraction and Visual Acuity	A monocular distance spherical over-refraction will be performed. The distance visual acuity to the nearest letter will be recorded OD, OS and OU.	Manual of Procedures [REDACTED]
11.	Subjective Lens Fit Assessment	
Lens centration, primary gaze movement, upgaze movement and tightness (push-up test) will be evaluated and graded.
 
The subject should not proceed to wear the contact lenses if any of the following is observed:
 
 • presence of limbal exposure (appearance of clear cornea) in any gaze • presence of edge lift • presence of unacceptable movement (excessive or insufficient) in all three movement categories (primary gaze, upgaze, and push-up). 
If either lens is deemed unacceptable, the
	Manual of Procedures [REDACTED]

		subject will be discontinued from the study. Remove the lenses, perform a slit-lamp evaluation, and complete the Final Evaluation form.	
12.	Visual Field Measurement	Esterman visual fields will be measured OD, OS and OU using a Humphrey perimeter.	Manual of Procedures

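### Assessor masking stops at the three binocular central acuity endpoints, so no masked operator is required for the Esterman fields, the eccentric targets or the simulation and game sessions

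*Combined protocol and SAP*

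**What the plan says.** **Masking.** Section 4.5 masks subjects to their sequence of lens wear. An unmasked investigator inserts and removes the lenses, and whoever records lens fit is also unmasked. For outcome collection, Section 4.5 says that "the identity of the study lenses will be masked to the investigator who will collect measurements for the study primary and secondary endpoints". Section 4.4 says: "Investigators who collect measurements for primary and secondary endpoints will also be masked to the identity of the study lenses". The synopsis and Section 2.4 carry the same limit.

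**Endpoints inside the rule.** Section 4.1 opens with "The primary endpoint will be measurements of binocular functional visual performance under distance day time conditions" and continues with "The secondary endpoints will be measurements of binocular functional visual performance measured under the following conditions". Together these are three measures, all binocular, central, high-contrast TCVA: distance at 250 cd/m², distance at 2.5 cd/m², and intermediate at 50 cd/m².

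**Measurements outside the rule.** Section 4.1 places the rest in a lower tier of other observations. Item vi is "Monocular and binocular horizontal visual fields when wearing the test and control contact lenses with an Esterman perimetry test". Items ii to v are the targets at 5°, 10° and 20°; item ii, for example, begins "Distance monocular and binocular functional visual performance of the test and control contact lenses under night time conditions". Items vii and viii are the subject's ratings after the driving simulation and the reaction-time game. Monocular central TCVA is item i.

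**Aim.** Section 3.1 states: "This pilot study will compare the central and peripheral visual performance, including functional assessment of vision".

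**Procedure.** In Section 4.7.1, at Visits 2 and 3, lens fit is step 11. Step 12 reads "Esterman visual fields will be measured OD, OS and OU using a Humphrey perimeter". Step 13 holds all TCVA and contrast testing, the simulation and the game. Neither step names an operator or sets a masking condition; both refer to the Manual of Procedures.

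**The concern.** The stated aim covers central and peripheral vision and functional assessment. The staff-masking rule covers only part of the central component. Every measurement that bears on peripheral vision, and every functional session, lies outside it.

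This matters because these are tests run by a person. Whoever runs a perimeter or an eccentric threshold test gives instructions, watches the subject's cooperation and may decide whether to repeat a run. An operator who knows which lens is on the eye, and expects or hopes against an effect of the ring, could shift the result in either direction. That mechanism is general reasoning about such tests; the protocol does not describe how they are conducted.

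The outcomes concerned have no margin and no pre-specified model. Section 9.1 plans descriptive summaries by lens type and allows further exploratory analysis. Their credibility therefore rests largely on how they were collected. A lens difference on them, or the absence of one, could be read as a property of the annulus when it partly reflects the operator.

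**Working it through.** The point turns on the scope of a rule. No alpha, power, effect size or SD enters, and the plan gives no figure to reproduce. The check sets the rule beside the procedures.

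**1. Sequence at Visits 2 and 3 (Section 4.7.1) against masking (Section 4.5)**

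| Step | Activity | Masking status of the operator |
|---|---|---|
| 6 | Lens type taken from the randomization scheme | Not stated for this step |
| 7 | Lens insertion | Unmasked |
| 8 | On-eye damage check | Not stated |
| 10 | Over-refraction and acuity with the lens on eye | Not stated |
| 11 | Lens fit | Unmasked |
| 12 | Esterman fields: right, left, both eyes | Not stated |
| 13 | Binocular central TCVA, 3 conditions | Masked |
| 13 | All other TCVA and contrast tests, simulation, game | Not stated |
| 14 | Lens removal | Unmasked |

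Step 12 stands on its own between the unmasked fit assessment and the step in which the masked investigator is first required.

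**2. How many results the rule reaches at one visit**

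- Step 13 conditions: 3 (distance, 2.5 cd/m²) + 1 (distance, 250 cd/m²) + 3 (intermediate, 50 cd/m²) = 7. Three are central and four eccentric (5° and 20° at 2.5 cd/m²; 5° and 10° at 50 cd/m²).
- Counting monocular viewing once: 7 × 2 = 14; adding 3 fields and 2 ratings gives 14 + 3 + 2 = 19. Eccentric results: 4 × 2 = 8.
- Counting right and left eyes separately, as the Esterman step does, and assuming that both eyes are tested: 7 × 3 = 21; 21 + 3 + 2 = 26. Eccentric results: 4 × 3 = 12.
- Covered by the rule: 3, under either count.

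So the rule reaches 3 of 19 or 3 of 26 results, depending on how eyes are counted. Either way it reaches none of the eccentric results and none of the 3 fields. These fractions describe the wording. They do not measure how many results would be collected unmasked, or the size of any bias.

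**3. Where the exposure is most plausible**

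- *Esterman fields:* clearest gap. This is a separate step, run by an operator, directly after unmasked work.
- *Eccentric targets and monocular central TCVA:* the wording leaves them open, but they share step 13 with the masked endpoints.
- *Driving and game ratings:* given by the masked subject, so an unmasked operator could act only through instructions or prompting.

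**4. Effect on the planned tests**

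The three non-inferiority comparisons in Section 9.1 use exactly the three endpoints inside the rule. They are untouched.

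**The case against.** The strongest reply is that the practical gap is much smaller than the wording suggests.

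- Step 13 groups central and eccentric, monocular and binocular testing by distance and luminance, and Section 4.5 randomizes the order of those settings. For an unmasked person to run only the eccentric targets, operators would have to change within a block, and nothing suggests that. One masked examiner probably runs all of it. **This stands**: the gap in step 13 is formal more than likely. The protocol still does not require it.
- A reader might infer that Section 4.5 masks nobody but the endpoint collector. It also masks the subject, and lenses are inserted by someone else for that purpose. **This stands**, and it confines the concern about ratings to prompting.
- A reader might infer that unmasked staff will run the fields, or will repeat poor ones. No section says so. The Manual of Procedures, whose text for these tests is not available here, may assign operators and set repeat rules. **This stands**: the finding is about what the protocol permits. If the Manual does assign a masked operator, the protocol's narrower statement should be brought into line with it.
- A reader might infer that the main conclusion is compromised. It is not: all three hypothesis tests lie inside the rule, and Sections 4.1 and 9.2 call every hypothesis exploratory.
- Tying masking to the endpoint hierarchy is a defensible choice in a pilot. **This stands in part**: the peripheral and functional measures sit low in the hierarchy, but Section 3.1 names them in the aim and Section 7.1 lists them among the efficacy parameters.

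**Conclusion.** The concern holds as a gap in scope. Four statements in the protocol limit staff masking to collectors of three binocular central TCVA measures. The unmasked investigator may therefore run the three Esterman fields at each measurement visit, and no masked operator is required for the eccentric targets or for the simulation and game sessions.

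The consequence is limited to the descriptive peripheral and functional results. The size of any operator effect cannot be estimated from the documents, and the counts above should not be read as if they did so. The documents do not support the stronger claims that these results will be collected unmasked, that the ratings are operator-determined, or that the non-inferiority conclusions are at risk.

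Two assumptions remain. The first is that the Manual of Procedures does not already assign a masked operator. The second is that the masked investigator can stay masked while working with a subject who may be wearing a lens with a 1 mm black annulus. That is a separate question, but the benefit of the fix depends on it. The change is worth making because it is cheap and protects results that the study says it wants.

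**What to change.** In Section 4.5, with matching wording in the synopsis and Sections 2.4 and 4.4:

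1. State that all step 12 and step 13 measurements at Visits 2 and 3 are run and recorded by the masked investigator. This covers the Esterman fields, all central and eccentric targets (monocular and binocular), the driving simulation, the game and the recording of the subject's ratings.
2. State that the unmasked investigator handles the randomization scheme and lens selection (step 6), insertion, the damage check, over-refraction and acuity with the lens on eye (step 10), fit assessment and removal, and takes no part in steps 12 and 13. Steps 6 and 10 need to be named. Left unassigned, step 6 could fall to the masked investigator and reveal the lens type.
3. Check that the Manual of Procedures assigns operators in the same way.

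**Cost.** Protocol wording and a division of duties between roles that Section 4.5 already requires; no new test. The downside is that the masked investigator also runs three perimetry fields per visit. The documents give no staffing plan for these visits of about 4.5 hours, so the site should confirm that this fits.
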